6.11.3 Week 8 OLE Visit

This visit will take place in-person at 56 ± 7 days after the Week 24 Visit of the placebo-controlled portion of the trial. The following procedures will be performed:

- Collect vital signs including weight
- Perform SVC
- Collect Home Spirometry
- Administer ALSFRS-R questionnaire
- CNS Bulbar Function Scale
- Collect blood samples for Clinical Safety Labs and, for WOCBP, for pregnancy test if applicable
- Review concomitant medications
- Assess and document AEs, including Key Study Events (*see section 10.3 of Master Protocol*)
- Administer the C-SSRS Since Last Visit questionnaire
- Dispense investigational product to participant
- Perform investigational product compliance
- Remind participant to bring investigational product to the next visit

6.11.4 Week 12 OLE Telephone Visit

This visit will take place via telephone at 84 ± 3 days after the Week 24 Visit of the placebo-controlled portion of the trial. The following procedures will be performed:

- Administer ALSFRS-R questionnaire
- Review concomitant medications
- Assess and document AEs, including Key Study Events (*see section 10.3 of Master Protocol*)
- Drug Compliance Check-In
- Remind participant to bring investigational product to the next visit

6.11.5 Week 16 OLE Visit

Participants should be instructed to hold study drug on the day of the study visit. Study drug should not be taken until after study visit procedures are complete.

This visit will take place in-person at 112 ± 7 days after the Week 24 Visit of the placebo-controlled portion of the trial. The following procedures will be performed:

- Collect vital signs including weight
- Perform SVC
- Collect Home Spirometry
- Administer ALSFRS-R questionnaire
- CNS Bulbar Function Scale
- Collect blood samples for Clinical Safety Labs and, for WOCBP, for pregnancy test if applicable
- Review concomitant medications
- Assess and document AEs, including Key Study Events (*see section 10.3 of Master Protocol*)
- Administer the C-SSRS Since Last Visit questionnaire
- Collect urine sample biomarker analyses
- Collect blood sample for biomarker analyses
- Whole blood PK and PD collection
- Plasma PD collection
- PD urine collection
- Dispense investigational product to participant
- Perform investigational product compliance
- Remind participant to bring investigational product to the next visit

6.11.6 Week 20 OLE Telephone Visit

This visit will take place via telephone at 140 ± 3 days after the Week 24 Visit of the placebo-controlled portion of the trial. The following procedures will be performed:

- Administer ALSFRS-R questionnaire
- Review concomitant medications
- Assess and document AEs, including Key Study Events (*see section 10.3 of Master Protocol*)
- Drug Compliance Check-In
- Remind participant to bring investigational product to the next visit

6.11.7 Week 24 OLE Telephone Visit

This visit will take place via telephone at 168 ± 3 days after the Week 24 Visit of the placebo-controlled portion of the trial. The following procedures will be performed:

- Administer ALSFRS-R questionnaire
- Review concomitant medications

- Assess and document AEs, including Key Study Events (*see section 10.3 of Master Protocol*)
- Drug Compliance Check-In
- Remind participant to bring investigational product to the next visit

6.11.8 Week 28 and Q12 Week OLE Visits

Participants should be instructed to hold study drug on the day of the study visit. Study drug should not be taken until after study visit procedures are complete.

The Week 28 OLE Visit will take place in-person 196 ± 14 days after the Week 24 Visit of the placebo-controlled portion of the trial. The procedures listed in the SoA should be performed and participants should be provided with 8 weeks of drug and instructions for dosing. Following the Week 28 OLE Visit, visit will occur every 12 weeks ± 14 days.

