²⁰ Drug accountability will not be done at phone visits. A drug compliance check-in must be held during phone visits to ensure participant is taking drug per dose regimen and to note any report of missed doses.

SCHEDULE OF ACTIVITIES – REGIMEN SPECIFIC OPEN LABEL EXTENSION PHASE (OPTIONAL)

Activity (page 1 of 1)	Master Protocol or Regimen-Specific	Open Label Extension (Optional) ⁵								
		Week 2	Week 4 ⁹	Week 8 ⁹	Week 12	Week 16 ^{8,9}	Week 20	Week 24	Week 28 and Q12 Weeks ^{8,9,11}	Follow-Up Safety Call ⁶
		Phone	Clinic	Clinic	Phone	Clinic	Phone	Phone	Clinic	Phone
		Day 14 ±3	Day 28 ±7	Day 56 ±7	Day 84 ±3	Day 112 ±7	Day 140 ±3	Day 168 ±3	Day 196 ± 14	28±7 days after last dose
Vital Signs ¹	Master		X	X		X			X	
Slow Vital Capacity	Master		X	X		X			X	
Home Spirometry	Regimen		X	X		X			X	
ALSFRS-R	Master		X	X	X	X	X	X	X	
ALSAQ-40	Regimen								X	
CNS Bulbar Function Scale	Regimen			X		X			X	
Clinical Safety Labs ²	Master		X	X		X			X	
PK/PD Biomarker Blood Collection ¹¹	Regimen					X			X ¹¹	
Biomarker PD Urine Collection ¹¹	Regimen					X			X ¹¹	
Biomarker Blood Collection ¹¹	Master					X			X ¹¹	
Biomarker Urine Collection ¹¹	Master					X			X ¹¹	
Concomitant Medication Review	Master	X	X	X	X	X	X	X	X	
Adverse Event Review ³	Master	X	X	X	X	X	X	X	X	X ⁶
Columbia-Suicide Severity Rating Scale	Master		X	X		X			X	

Administer/Dispense Investigational product	Master			X		X			X	
Drug Accountability/Compliance	Master	X ¹⁰	X	X	X ¹⁰	X	X ¹⁰	X ¹⁰	X	

¹ Vital signs include weight, systolic and diastolic pressure, respiratory rate, heart rate and temperature. Height in cm measured at Master Protocol Screening Visit only.

² Clinical safety labs include hematology (CBC with differential), complete chemistry panel, liver function tests, thyroid function and urinalysis. Serum pregnancy testing will occur in women of child-bearing potential at the Master Protocol Screening Visit and as necessary during the study. Pregnancy testing is only repeated as applicable if there is a concern for pregnancy.

³ Adverse events that occur after signing the consent form will be recorded.

⁴ Participants who continue into OLE will have a Follow-Up Safety Call (as described in the body of this RSA) after their last dose of study drug during the OLE phase.

⁵ The duration of the OLE is until the primary results of the 24 week double-blind portion of the study are available, or Clene or sponsor terminates support or development of CNM-Au8 for ALS.

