⁶ Participants who continue into the OLE and then withdraw consent or early terminate will be asked to complete an Early Termination Visit and Follow-Up Safety Call as described in the body of this RSA.

⁷ The maximum window between study visits during the OLE may not exceed 64 days for the Week 8 and Week 16 visits; and 96 days for the Week 28, Week 40, and Week 52 visits.

⁸ Participants should be instructed to hold the study drug on the day of the study visit. Study drug should not be taken until after study visit procedures are complete.

⁹ Visit may be conducted via phone or telemedicine with remote services instead of in-person if this is needed to protect the safety of the participant due to a pandemic or other reasons.

¹⁰ Drug accountability will not be done at phone visits. A drug compliance check-in must be held during phone visits to ensure participant is taking drug per dose regimen and to note any report of missed doses

¹¹ Blood and urine biomarker collection in OLE phase will only occur at week 16, 28, and 52

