1.2 CNM-Au8 Therapeutic Rationale

CNM-Au8 is a concentrated aqueous suspension of clean-surfaced nanocrystals consisting solely of Au atoms organized into clean surfaced crystals of highly faceted, substantially uniform geometrical shapes that act as nanocatalysts, supporting cellular bioenergetic reactions.

CNM-Au8 is supplied for dosing orally in sodium bicarbonate buffered USP purified water. Each mL of CNM-Au8 suspension at 500 µg/mL is estimated to contain between 100 - 500 trillion highly faceted Au nanocrystals. IP will consist of 60 mL high density polyethylene (HDPE) bottles containing CNM-Au8 at concentrations of 250 µg/mL (15 mg) or 500 µg/mL (30 mg), or placebo, administered orally, once daily in the morning, at least 30 minutes prior to food intake. Study participants will consume two (2) bottles of IP each morning for total daily intake of 120 mL equivalent to CNM-Au8 30mg or 60mg, or placebo.

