5.4 Study Medication/Intervention, Administration, Escalation, and Duration

Participants will either receive CNM-Au8 30 mg, 60 mg, or color-matched placebo in the study. The Investigational Product (IP) will be self-administered by participants who will be directed to take the IP each day in the morning at approximately the same time, at home at least thirty (30) minutes prior to food intake. The drug formulations will be identical in appearance (size, shape, volume, color) and smell. The packaging and labeling will be designed to maintain blinding to the Site Investigator's team and to participants. There are no visible differences between CNM-Au8 30 mg, 60 mg, and placebo dosing units.

Participants may take the study drug by mouth or through a gastric tube. Participants taking study drug by gastric tube should be directed to first flush the tube with approximately 20-30 mL of distilled water, administer study drug, and then flush the tube post-study drug administration with another 20-30 mL of distilled water.

Based on the supply of the IP provided, the maximum window between in-clinic study visits during the placebo-controlled period may not exceed 64 days. The maximum window between in-clinic study visits during the Open Label Extension period may not exceed 64 days for the first 16 weeks, and may not exceed 96 days for the duration of the OLE study period.

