5.5 Dosage Adjustment

No dosage adjustments are anticipated during the placebo-controlled period of the study. If participants have difficulty tolerating IP, the Investigator may permit the participants to reduce the daily dose by one (1) bottle. Potential tolerability issues may include gastrointestinal disturbances, headache, somnolence, or other treatment emergent adverse events are not otherwise explained.

Down titration of IP to one (1) bottle daily will only be allowed to address tolerability issues and only with Medical Monitor approval. After a participant has been down titrated to, he/she may be allowed to retry two (2) bottle dose (re-challenge), after a discussion with and approval by the Site Investigator and Medical Monitor. Any dosing changes must be appropriately documented including start date(s) and re-challenge date(s). If the participant cannot tolerate the re-challenge, he/she may remain at the lower dose of one (1) bottle daily. Drug holidays (e.g., treatment-free periods) are not permitted.

During the Open Label Extension, participants will maintain their current blinded dose. Participants previously randomized to placebo during the placebo-controlled period of the study will be re-randomized to receive CNM-Au8 30 mg or 60 mg for the Open Label Extension. All dosing assignments will remain blinded throughout the Open Label Extension. IP tolerability issues encountered during the Open Label Extension will be managed on a case-by-case basis by the Site Investigator in coordination with the Medical Monitor.

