6.11 Open Label Extension

Participants who have completed the placebo-controlled portion of the trial on drug, will be eligible to continue in the Open Label Extension (OLE) as outlined in the SOA. Participants will first be asked about their desire to continue in the OLE at the Regimen-Specific Screening Visit. They will also be asked to *re-confirm* whether they want to continue in the OLE at the Week 16 Visit of the placebo-controlled period. The OLE, CNM-Au8 will be provided by Clene Nanomedicine, until the primary results of the 24 week double-blind portion of the study are available, or Clene or sponsor terminate support or development of CNM-Au8 for ALS.

Modifications to OLE Schedule

Designated visits in the Schedule of Activities for the OLE (i.e. Week 4, Week 8, Week 16, Week 28, and Week 40) may be conducted via telemedicine (or phone if telemedicine is not available) with remote services instead of in-person if needed to protect the safety of the

participant due to a pandemic or other reason. If a planned in-clinic visit is conducted via telemedicine (or phone if telemedicine is not available) with remote services, only selected procedures will be performed. Instructions on how to document missed procedures are included in the Manual of Procedures.

In addition to the procedures in the Master Protocol that should be conducted during the phone or telemedicine and remote visits, the following regimen-specific procedures should be completed:

- Home Spirometry
- CNS Bulbar Function Scale (Not done at OLE Week 4).

Blood and urine samples for PK and PD analysis are **not** collected during the remote visits by the home health agency, and this should be recorded as such in the applicable source documentation and EDC.

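### The 8-week drug supply specified at OLE Week 28 does not cover the 12 weeks to the next dispensing visit: 28 days short at two bottles a day

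*Protocol*

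**What the plan says.** Protocol Section 6.11.8, on the OLE Week 28 visit, states that "participants should be provided with 8 weeks of drug and instructions for dosing". The next sentence reads "Following the Week 28 OLE Visit, visit will occur every 12 weeks ± 14 days".

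The other relevant provisions are:

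- **Dispensing points.** In the OLE Schedule of Activities, the row "Administer/Dispense Investigational product" is marked at Week 8, Week 16, and the combined column for Week 28 and every 12 weeks after it. Nothing is marked between Week 28 and Week 40.
- **Longest gap between visits.** Section 5.4 says that after the first 16 OLE weeks the gap between in-clinic visits "may not exceed 96 days for the duration of the OLE study period". Footnote 7 of the OLE schedule gives 64 days for Weeks 8 and 16, "and 96 days for the Week 28, Week 40, and Week 52 visits".
- **Daily use.** Section 1.2: "Study participants will consume two (2) bottles of IP each morning for total daily intake of 120 mL". Section 5.5 (Dosage Adjustment): "During the Open Label Extension, participants will maintain their current blinded dose".
- **Duration of supply.** Section 6.11 says drug will be provided "until the primary results of the 24 week double-blind portion of the study are available", or until support or development ends.

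**The concern.** The supply instruction and the visit interval stand in consecutive sentences and do not agree. A site that follows Section 6.11.8 exactly gives a fully dosed participant about two thirds of the drug needed to reach the next dispensing visit.

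The result would be an unplanned treatment gap of about four weeks after Week 28, in an extension meant to supply drug until the primary results are available. Section 5.5 (Dosage Adjustment) rules out drug holidays. That sentence comes before the section's OLE paragraph, but nothing in the OLE text allows a planned gap. The Week 40 assessments, including ALSFRS-R, slow vital capacity and safety labs, would then be made after about 28 days off drug.

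The quantity for later 12-weekly visits is not clearly stated either. The sentence is about Week 28, although the section heading and the schedule column cover the later visits too. A site that repeated 8 weeks of supply at Week 40 would recreate the gap before Week 52, when blood and urine biomarkers are collected.

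**Working it through.** **Inputs.** Supply at Week 28: 8 weeks (Section 6.11.8). Interval to the next visit: 12 weeks ± 14 days (Section 6.11.8). Longest gap: 96 days (Section 5.4; OLE schedule footnote 7). Full dose: 2 bottles a day (Section 1.2; Table 2). Week 16 is Day 112 and Week 28 is Day 196 (OLE schedule).

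**Stated supply.** 8 × 7 = 56 days; 56 × 2 = 112 bottles.

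**Need and shortfall at two bottles a day** (shortfall = interval − 56 days):

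| Interval to next visit | Days | Bottles needed | Shortfall |
|---|---|---|---|
| Earliest, window counted from the previous visit (84 − 14) | 70 | 140 | 14 days, 28 bottles |
| Nominal (12 × 7) | 84 | 168 | 28 days, 56 bottles |
| Longest permitted gap | 96 | 192 | 40 days, 80 bottles |

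At the nominal interval the supply covers 56/84 = 67% of the days.

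**Fixed-calendar reading of the window.** Section 6.11.8 does not say whether the 14 days run from the previous visit or from a fixed calendar. On a fixed calendar the nominal Week 40 day is 196 + 84 = 280. If Week 28 is as late as allowed (196 + 14 = 210) and Week 40 as early as allowed (280 − 14 = 266), the interval is 266 − 210 = 56 days and the shortfall is 0. Every other combination leaves a gap.

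**Supply with a buffer (assumption).** The 64-day limit in the 8-weekly phase suggests that an 8-week supply might in practice cover 64 days. The shortfall is then 84 − 64 = 20 days at the nominal interval and 96 − 64 = 32 days at the maximum.

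**Reduced dose.** At one bottle a day, 112 bottles last 112 days, which exceeds 96, so there is no shortfall.

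**Possible origin.** Eight weeks matches the earlier dispensing interval: Week 8 to Week 16 is 112 − 56 = 56 days. But Week 16 to Week 28 is already 196 − 112 = 84 days with no dispensing marked between, so the schedule needs a 12-week supply even before Week 28.

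**Window against maximum.** 84 + 14 = 98 days, 2 days over the 96-day limit.

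**The case against.** The strongest reply is that this is one stale figure set against several consistent provisions. Section 5.4 introduces its visit-gap limits by reference to the drug supplied and then allows 96 days in the later OLE; footnote 7 agrees. On this view the supply design is sound, sites would notice, and the Manual of Procedures may provide for interim shipments, particularly since Section 6.11 lets Weeks 28 and 40 be held remotely. The shortfall also depends on the reading: 20 days rather than 28 at the nominal interval under the 64-day assumption, and none at one bottle a day or in the extreme fixed-calendar case.

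Much of this stands as a limit on consequence. Whether any participant would actually run out cannot be settled from these documents, and the figure may well be a carry-over from the 8-weekly phase. Section 5.4 also attaches its supply clause to the sentence on the placebo-controlled period, so the link to the OLE limit is inferred from its position in the same paragraph.

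None of it makes the instruction right. The agreement of Section 5.4 and footnote 7 on 96 days is evidence that 8 weeks is the wrong figure. An unseen manual might work around the text but would not correct it.

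**Conclusion.** The concern holds. Followed as written, Section 6.11.8 leaves a participant on two bottles a day 28 days (56 bottles) short at the nominal 12-week interval and 40 days (80 bottles) short at the 96-day maximum. These figures assume that 8 weeks means 56 days, that dosing is at the full two bottles, and that no drug is supplied between scheduled dispensing points. On the 64-day assumption the gap is 20 to 32 days. It disappears only at the reduced dose or at the extreme of the fixed-calendar window.

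The effect is confined to continuity of dosing in the optional OLE. No comparison in the 24-week placebo-controlled period is touched. The text should still be corrected: it is an explicit dispensing instruction that conflicts with the protocol's own visit interval.

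**What to change.** In Section 6.11.8, replace the 8-week figure with a supply that covers the longest permitted interval: 96 days, or 192 bottles at two a day. State that this applies at Week 28 and at every 12-weekly visit after it. Twelve weeks (168 bottles) would be the minimum correction, but it leaves 96 − 84 = 12 days uncovered when a visit falls at the maximum gap. If the larger quantity is hard to handle, the alternative is to keep 8 weeks and add an interim shipment or dispensing point to the schedule. It would also help to say that the 96-day maximum overrides the upper end of the ± 14-day window.

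The cost is one figure and one sentence in the protocol and a supply instruction to sites, plus the handling of a larger quantity per visit.

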7 OUTCOME MEASURES AND ASSESSMENTS

For all assessments listed below, please refer to the Manual of Procedures for detailed instructions.

7.1 Voice Analysis

In addition to the scheduled in clinic voice recordings, voice samples will be collected twice per week, using an app installed on either an android or iOS based smartphone. The app characterizes ambient noise, then asks patients to perform a set of speaking tasks: reading sentences -- 5 fixed and 5 chosen at random from a large sentence bank-- repeating a consonant-vowel sequence, producing a sustained phonation, and counting on a single breath. Voice signals are uploaded to a HIPAA-compliant web server, where an AI-based analysis identifies relevant vocal attributes. Quality control (QC) of individual samples will occur by evaluation of voice records by trained personnel.

The voice analysis app is only available in English, therefore participants who do not speak English should not complete the voice recording. Caregivers cannot provide language assistance when the participant is completing the voice recording.

7.2 ALSAQ-40

The Amyotrophic Lateral Sclerosis Assessment Questionnaire-40 (ALSAQ-40) is a patient self-report health status patient-reported outcome. The ALSAQ-40 consists of forty questions that are specifically used to measure the subjective well-being of patients with ALS and motor neuron disease.

Participants will be handed the questionnaire and asked to write their answers themselves. Caregivers can also help, if needed.

7.3 Center for Neurologic Study Bulbar Function Scale

The Center for Neurologic Study Bulbar Function Scale (CNS-BFS) is a patient self-report scale that has been developed for use as an endpoint in clinical trials and as a clinical measure for evaluating and following ALS patients. The CNS-BFS consists of three domains (swallowing, speech, and salivation), which are assessed with a 21-question, self-report questionnaire.

Participants will be handed the questionnaire and asked to write their answers themselves. Caregivers can also help, if needed.

Instructions on administering the questionnaire during a phone or telemedicine visit will be included in the MOP.

7.4 Home Spirometry

Remote/home-based forced vital capacity will be measured with the MIR Spirobank Smart spirometer. Instructions for use will be provided to the participant. The participant will perform the vital capacity maneuver at home (or other remote location) with real time video coaching (or phone coaching, if video is not available) by the evaluator. Three to five vital capacity maneuvers will be performed, consistent with the manner vital capacity is obtained in clinic.

8 BIOFLUID COLLECTION

8.1 Pharmacokinetic (PK) Assessments

8.1.1 Whole Blood PK Assessments of CNM-Au8

Samples for the measurement of whole blood concentrations of Au will be collected before (pre-dose) administration of investigational product per the Schedule of Assessments. PK collection and processing parameters are specified in the RSA laboratory manual.

PK analyses of CNM-Au8 will be specified in a separate PK analysis plan.

PK blood samples will be shipped to and analyzed under the responsibility of the Clene Nanomedicine, Inc.'s bioanalytical laboratory at:

Clene Nanomedicine, Inc.
Bioanalytics Laboratory
[name] [name] 21901-2912
USA

8.1.2 Plasma PK Assessments of Riluzole

Samples for the measurement of plasma concentrations of riluzole will be collected before (pre-dose) administration of both riluzole and the IP per the Schedule of Assessments. Riluzole plasma PK collection and processing parameters are specified in the laboratory manual.

Population PK analyses of riluzole will be specified in the separate PK analysis plan. The first forty (40) participants taking riluzole and randomized to Regimen C (CNM-Au8) to reach the Week 8 visit will be evaluated by the DSMB, or unblinded DSMB PK designee, to determine whether there are any changes in riluzole population PK parameters following treatment with CNM-Au8 versus placebo at the Week 4 and Week 8 timepoints. The unblinded riluzole population PK analyses and designee will be implemented as per the DSMB charter.

Riluzole PK plasma samples will be shipped to and analyzed under the responsibility of Covance Central Laboratory Services LP.

